2. OUTCOME MEASURES

Primary outcome

All-cause mortality within 90 days following surgery

Secondary outcomes

- All-cause mortality within 180 days following surgery
- Duration of hospital stay (defined as the number of days from surgery until hospital discharge)
- Hospital re-admission within 180 days of surgery

The start of surgery will be defined as when the patient enters the operating theatre or anaesthetic room.

Process measures

- 1. Consultant led decision to operate
- 2. When consultant led decision to operate, did this consultant personally review patient at time of decision?
- 3. Preoperative documentation of risk
- 4. Time from decision made to operate to entry into operating theatre
- 5. Patient entered operating theatre within time-frame specified based on their urgency level (i.e. <2 hours, 2-6 hours, 6-18 hours, or >18 hours)
- 6. Consultant surgeon present in operating theatre
- 7. Consultant anaesthetist present in operating theatre
- 8. Goal directed fluid therapy used during surgery
- 9. Arterial lactate measured at end of surgery
- 10. Critical care admission immediately after surgery

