Prospectively collected data from the recently published Emergency Laparotomy Network study in 35 NHS hospitals closely match our inclusion/exclusion criteria and describe a median of 184 eligible patients aged \geq 40 years per hospital per year (range 32-736). Data from the Hospital Episodes Statistics database for the year ending April 2011 gives average 90-day mortality as 25%. These data have been used to estimate the baseline mortality rate and between hospital coefficient of variation. Power calculations are based on the methodology proposed by Hussey & Hughes, for an analysis with fixed time effects and random cluster effects, modified to exclude data collected during the five week period in which the intervention commences in individual hospitals. The trial will be conducted in at least 90 NHS hospitals over a period of 85 weeks during which time we expect to receive data describing 27,540 patients undergoing emergency laparotomy. For a baseline 90-day mortality of 25%, between hospital coefficient of variation of 0.15, constant case-load (18 patients per 5 weeks per hospital) and assuming independent hospital effects, the study would achieve 92% power to detect a 12% relative risk reduction in mortality from 25% to 22% (two-sided p<0.05). This calculation is insensitive to the coefficient of variation but sensitive to the effect size. In practice, power may be reduced by correlation between hospitals within geographic areas and by variation in case-load between hospitals. The worst case scenario is one where each of the 15 geographic areas functions effectively as a single large hospital, reducing the power to 83%. This figure incorporates an adjustment for variable case-load from the pilot data. Thus the power of the study to detect a 12% relative risk reduction lies between 83% and 92%.

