For analysis of the primary and secondary outcomes, the following summaries will be provided:

- The number of patients included in the analysis, by treatment group
- The number of hospitals included in the analysis
- A summary statistic for the outcome (e.g. the number (%) of patients experiencing an event for binary outcomes)
- The estimated treatment effect with its 95% confidence interval and a two-sided p-value

The significance level is set at 5%. All analyses will include time-period in the model as a fixed-effect using indicator variables. All analyses will adjust for age, gender, and indication for surgery (peritonitis, perforation, abdominal infection, intestinal obstruction, haemorrhage, ischaemia, other, or multiple indications) using fixed factors. Age will be included as a continuous covariate, and will be assumed to have a linear association with the outcome. Missing baseline data will be imputed using mean imputation for continuous variables (age), and using a missing indicator for categorical variables (gender, indication for surgery) (based on guidance from White IR, Thompsons SG. *Adjusting for partially missing baseline measurements in randomized trials.* Stat Med 2005).

Primary outcome

The primary outcome (all-cause mortality up to 90 days following surgery) will be analysed using a mixed-effects parametric survival model, with a Weibull survival distribution. This model will include random-intercepts for geographical area, hospital, and the interaction between hospital and time-period. Time-period will be included in the model as a fixed-effect using indicator variables. Age, gender, and indication for surgery will also be included in the model as fixed factors.

Note that we are including the interaction between hospital and time-period as a random-effect as recent research has indicated this is required in order to preserve type I error rates at the nominal level (i.e. Morgan K, Forbes A, Keogh R, Jairath V, Kahan B. *Choosing appropriate analysis methods for cluster randomised cross-over trials with a binary outcome.* Accepted.)

An example dummy dataset is provided in table 1 and example Stata code is provided below to demonstrate how this analysis will be implemented.

Example Stata code

stset time_to_outcome, failure(outcome)

mestreg treatment i.time_period age gender i.indication_surgery || geo_area: || hospital: || hospital_time_period: , distribution(weibull)

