If there are convergence issues with this analysis approach, we will use the strategy shown in table 2 to find an analysis approach which converges.

Table 1 – Example dataset

| Geographical | Hospital | Time period | Hospital*time | Treatment | Patient |
|--------------|----------|-------------|--------------------|-----------|---------|
| area | | | period interaction | | |
| 1 | 1 | 1 | 1 | 0 | 1 |
| 1 | 1 | 1 | 1 | 0 | 2 |
| 1 | 1 | 2 | 2 | 0 | 3 |
| 1 | 1 | 2 | 2 | 0 | 4 |
| 1 | 2 | 1 | 3 | 0 | 5 |
| 1 | 2 | 1 | 3 | 0 | 6 |
| 1 | 2 | 2 | 4 | 0 | 7 |
| 1 | 2 | 2 | 4 | 0 | 8 |
| 2 | 3 | 1 | 5 | 0 | 9 |
| 2 | 3 | 1 | 5 | 0 | 10 |
| 2 | 3 | 2 | 6 | 1 | 11 |
| 2 | 3 | 2 | 6 | 1 | 12 |
| 2 | 4 | 1 | 7 | 0 | 13 |
| 2 | 4 | 1 | 7 | 0 | 14 |
| 2 | 4 | 2 | 8 | 1 | 15 |
| 2 | 4 | 2 | 8 | 1 | 16 |

Table 2 – Analysis approaches to be used if the primary method of analysis fails to reach convergence

| | Change from previous strategy | Example Stata code |
|---|--|---|
| 1 | Remove the random-effect for the hospital/time-period interaction | mestreg outcome treatment i.time_period age gender i.indication_surgery geo_area: hospital: , distribution(weibull) |
| 2 | Remove the random-effect for hospital | mestreg outcome treatment i.time_period age gender i.indication_surgery geo_area: , distribution(weibull) |
| 3 | Adjust for the fixed-effect of time as a continuous covariate using restricted cubic splines with 7 knot points (where rcs_time_period* are the variables forming the restricted cubic spline) | mestreg outcome treatment rcs_time_period* age gender i.indication_surgery geo_area: , distribution(weibull) |

Secondary outcomes

All-cause mortality up to 180 days

All-cause mortality up to 180 days following surgery and hospital re-admission within 180 days of surgery will be analysed using the same approach as the primary outcome.

Duration of hospital stay

Duration of hospital stay will be analysed using a competing-risk time-to-event model, which recognises mortality as a competing risk for hospital discharge. Because there are no facilities for analysing competing risk data using mixed-effects models in Stata, we will use robust standard errors which account for clustering by geographical area. This analysis will be implemented in Stata as follows:

stset cc_time_to_discharge, failure(cc_discharge == 1)

stcrreg treatment i.time_period age gender i.indication_surgery, compete(cc_discharge == 2) vce(cluster geo_area)

Where:

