cc_discharge is a variable indicating whether the patient was discharged home (=1), died in hospital (=2), or was censored (=0), and *cc_time_to_discharge* is a variable indicating the time to the event.

Hospital re-admission within 180 days

This outcome will be analysed using a competing-risk time-to-event model, which recognizes mortality as a competing risk for hospital re-admission. It will be implemented using the same code as *duration of hospital stay* above.

Secondary analyses of the primary outcome

Evaluating the effect of the intervention over time

We will perform a secondary analysis of the primary outcome to evaluate the effect of the intervention over time (i.e. whether the intervention effect improves over time). This analysis will include patients who presented to hospital during the 5-week period immediately after implementation of the quality improvement intervention. We will evaluate the following four groups:

- Usual care;
- The quality improvement (QI) intervention implemented for less than 5 weeks
- The QI intervention was implemented for 5 weeks or more and less than 10 weeks
- The QI intervention was implemented for 10 weeks or more

This analysis will allow us to determine whether the effectiveness of the QI intervention improves over time. The analysis will be implemented using the same method as for the primary analysis of the primary outcome.

Inclusion of other patient populations which may be affected by the intervention

We will perform a sensitivity analysis to assess whether results are generalisable to other patient populations which may have been affected by the intervention. This includes patients who underwent laparoscopic surgery, and patients who are aged 18-40 years.

Due to the small number of patients in these groups, we will summarise results descriptively, rather than undertaking a formal statistical analysis. We will summarise the number (%) of patients in the treatment arms who experience a primary outcome event. The denominator for this analysis will include patients who either underwent laparoscopic surgery or were aged 18-40 years (or both), and who met all other eligibility criteria.

Process measures

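### The only adjusted estimate for length of stay, and on the more specific reading for re-admission, is a subdistribution hazard ratio that a mortality benefit alone would move above 1

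*SAP*

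**What the plan says.** Section 2 defines the outcome in days: "Duration of hospital stay (defined as the number of days from surgery until hospital discharge". Section 5 then sets the model: "Duration of hospital stay will be analysed using a competing-risk time-to-event model, which recognises mortality as a competing risk for hospital discharge". The code is `stcrreg` with in-hospital death as the competing event, and Appendix 3 censors patients still in hospital at day 60.

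For re-admission, the outcome's own subsection of section 5 says: "This outcome will be analysed using a competing-risk time-to-event model, which recognizes mortality as a competing risk for hospital re-admission". It refers back to the same code. The list of changes from protocol in section 1 agrees, and so does Appendix 3, which codes death before re-admission as a separate state. Time runs from surgery. However, the section 5 paragraph on 180-day mortality also names re-admission and assigns it to the primary outcome's method, a mixed-effects Weibull model. The SAP therefore gives two different models for re-admission.

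Under the general principles of section 5, each outcome also gets a summary statistic by group, an effect estimate with 95% confidence interval, and a p-value. The form of the summary is not fixed for stay or re-admission. Neither outcome has a planned cause-specific model or cumulative incidence curve. The SAP does not say how the subdistribution ratio is to be interpreted.

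**The concern.** A Fine-Gray model keeps patients who have died in the risk set as people who never have the event. Its ratio therefore describes cumulative incidence: the chance of having left hospital alive, or of having been re-admitted, by a given day. It does not describe how quickly survivors leave or how often they return.

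That matters here because the trial aims to change the competing event. Each death avoided moves a patient from never discharged to discharged, and later into the group that can be re-admitted. Both ratios then rise with no change in discharge or re-admission rates among patients alive and at risk. A ratio above 1 looks favourable for discharge and unfavourable for re-admission. If the trial succeeds on mortality, the planned estimates alone would not show whether stay or re-admission had changed beyond the change in survival.

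**Working it through.** **1. The SAP's own power figure.** Inputs from section 3: "For a baseline 90-day mortality of 25%, between hospital coefficient of variation of 0.15, constant case-load (18 patients per 5 weeks per hospital"), two-sided 5%, 90 hospitals, 15 steps, 17 periods, transition period dropped ("modified to exclude data collected during the five week period in which the intervention commences in individual hospitals"). The method is Hussey and Hughes, with fixed period effects and a random hospital effect.

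- Between-hospital SD = 0.15 × 0.25 = 0.0375.
- Cell variance = 0.25 × 0.75 / 18 = 0.01042.
- Resulting standard error of the risk difference = 0.00885.
- Power = Φ(0.03/0.00885 − 1.96) = Φ(1.43) = 92.3%.

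With the cell variance taken at 23.5%, power is 93.2%. The stated 92% is reproduced, so the design inputs are understood. The SAP states no corresponding figure for stay or re-admission.

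**2. The planned mortality effect as a hazard ratio.** The SAP plans for this: "the study would achieve 92% power to detect a 12% relative risk reduction in mortality from 25% to 22"%. Under proportional hazards, death HR = ln(0.78)/ln(0.75) = 0.864.

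**3. Effect on the planned estimate.** The check was a two-arm simulation without period effects, with 4,000,000 patients per scenario. The death hazard was multiplied by 0.864, and the discharge or re-admission hazard was identical in both arms. With administrative censoring only (day 60 or 180), Fine-Gray equals a Cox fit with deaths held in the risk set to the horizon. The cause-specific fit censors deaths. In-hospital mortality, 180-day mortality, re-admission risk and the stay distribution are not in the SAP, so all are assumptions shown as ranges.

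Discharge alive:

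| Assumed in-hospital mortality | Subdistribution HR | Cause-specific HR | Mean stay of survivors, control vs intervention (days) |
|---|---|---|---|
| 10% | 1.032 | 0.999 | 12.23 vs 12.30 |
| 15% | 1.044 | 0.998 | 11.99 vs 12.09 |
| 20% | 1.057 | 1.001 | 11.75 vs 11.87 |
| 25% | 1.068 | 1.001 | 11.49 vs 11.64 |

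The subdistribution HR rises while survivors' mean stay lengthens slightly.

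**4. Rescued patients discharged late** (assumed after day 25), over the same mortality range. The subdistribution HR is 1.018 to 1.045, the cause-specific HR is 0.981 to 0.964, and survivors' mean stay rises by 0.3 to 0.8 days. The planned ratio then points opposite to survivors' actual stay.

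**5. Re-admission.** Assumed 180-day mortality was 25% to 32%, and re-admission risk in the absence of death 20% to 40%. The subdistribution HR is 1.026 to 1.044 and the cause-specific HR 0.996 to 1.003. The share re-admitted rises by 0.4 points (16.7% to 17.1%) to 1.2 points (31.3% to 32.4%, before rounding). Hand check at 30% and 25%: ln(1 − 0.2569)/ln(1 − 0.2501) = 1.032, against 1.031 simulated.

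**6. Could this shift alone reach p<0.05?** Analysed patients = 90 × 16 × 18 = 25,920. Within-period treatment variance: periods 2 to 16 each have 14 areas outside transition, k of them treated (k = 0 to 14). The variance is Σ k(14 − k)/14 divided by 240 area-periods = 32.5/240 = 0.135. Chance = Φ(√(25,920 × event share × 0.135) × ln HR − 1.96), treating patients as independent.

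- Stay (assumed 80% discharged alive): 35% at HR 1.03 and 73% at 1.05. With an assumed design effect of 2, these fall to 20% and 45%.
- Re-admission (assumed 22% re-admitted): 13% at 1.03 and 19% at 1.04. With a design effect of 2, these fall to 8% and 12%.

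**The case against.** Fine-Gray with death as the competing event is a recognised method, and section 1 records it as a deliberate replacement for a simple time-to-event model. The SAP says openly that mortality competes with discharge. It nowhere equates a ratio above 1 with shorter stay. This stands: the choice of model is not an error.

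A reader might infer that a success on mortality would produce a spurious benefit on stay and a spurious harm on re-admission. The documents do not support that. If fewer patients die, more really do go home and more really are re-admitted, and the ratio describes this correctly. For re-admission the shift would seldom be significant alone.

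Nor are these outcomes judged by the ratio alone. Group summaries are planned, and both mortality results sit in the same dummy table. That help is limited. The summaries are unadjusted, and in a stepped-wedge design they are mixed with calendar time, which the SAP itself says of its Kaplan-Meier plot. Seeing mortality alongside alerts the reader but does not separate the effects.

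The strongest objection is that the cause-specific ratio is not clean either. It fell to 0.96 when rescued patients left late. In another simulation, with a death reduction of about 12%, in-hospital mortality of about 18% to 19% and stay unrelated to severity, it was 1.019 against a subdistribution ratio of 1.058. For re-admission, time from surgery counts inpatients as at risk, so the ratio also moves with discharge timing. This stands too, and is why conclusions should not rest on the cause-specific ratio alone.

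**Conclusion.** The point holds in limited form. For stay, the only adjusted estimate answers a different question from the one the outcome definition poses. The same is true of re-admission under its own subsection and the list of changes from protocol. If the Weibull sentence governed and deaths were censored, re-admission would instead have a cause-specific estimate, so that half depends on reconciling the passages.

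At the planned mortality effect the shift is modest: about 3% to 7% for discharge and 3% to 4% for re-admission. For stay it is large enough to reach significance in a fair share of trials before clustering is allowed for. These figures rest on the assumed mortality, stay and re-admission ranges, on proportional hazards for death, and on applying the 90-day death hazard ratio to in-hospital and 180-day deaths. The direction follows from the model itself. The remedy is additional reporting and a rule for interpretation; the planned model need not be replaced.

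**What to change.** Keep the subdistribution hazard ratio. For both outcomes, add:

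- the cause-specific hazard ratio, with deaths censored and the same covariates, fitted in `mestreg` with the random effects already specified for the primary outcome;
- the cumulative incidence of the event and of death, by arm.

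The `stset` line for stay already declares discharge as the only failure, so the cause-specific model needs little new code. It can also carry the hospital-by-period random effect, which the SAP considers necessary for type I error and which `stcrreg` cannot include.

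Add a short paragraph stating that the subdistribution ratio combines effects on survival and on the event. It should say that a conclusion about stay or re-admission requires both ratios to be read together with mortality, because the cause-specific ratio can also shift if rescued patients differ from other survivors.

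Reconcile the sentence assigning re-admission to the primary outcome's method with the re-admission subsection and the list of changes from protocol.

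The cost is two extra model fits, the incidence curves and a paragraph of text. The drawback is two ratios per secondary outcome to explain.

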Appendix 1: Dummy tables

Table 1 – Patient characteristics

| | Missing | g data | Summary | Summary measure | |
|---|--------------|-----------|--------------|-----------------|--|
| | Intervention | Control – | Intervention | Control | |
| | – no. (%) | no. (%) | (n=) | (n=) | |
| Baseline characteristics | | | | | |
| Female – no. (%) | | | | | |
| Age – mean (SD) | | | | | |
| Indication for surgery – no. (%) | | | | | |
| Peritonitis | | | | | |
| Perforation | | | | | |
| Abdominal infection | | | | | |
| Intestinal obstruction | | | | | |
| Haemorrhage | | | | | |
| Ischaemia | | | | | |
| Other | | | | | |
| Pre-operative characteristics | | | | | |
| Estimated risk of death – no. (%) | | | | | |
| Low (<5%) | | | | | |
| Medium (5-10%) | | | | | |
| High (>10%) | | | | | |
| Not documented | | | | | |
| ASA score – no. (%) | | | | | |
| 1 (no systemic disease) | | | | | |
| 2 (mild systemic disease) | | | | | |
| 3 (severe systemic disease, not life | | | | | |
| threatening) | | | | | |
| 4 (severe, life threatening) | | | | | |
| 5 (moribund patient) | | | | | |
| P-POSSUM score – mean (SD) | | | | | |
| Blood lactate (mmol/l) – mean (SD) | | | | | |
| Systolic blood pressure (mmHg) – mean (SD) | | | | | |
| Glasgow coma scale – mean (SD) | | | | | |

Table 2 – Main results for primary and secondary outcomes

| | Missing data | Missing data | Summary | Summary | Treatment | P-value |
|----------------------|----------------|--------------|----------------|-----------|-------------|---------|
| | (intervention) | (control) | measure | measure | effect (95% | |
| | | | (intervention) | (control) | CI) | |
| All-cause mortality | | | | | | |
| up to 90 days from | | | | | | |
| surgery (primary | | | | | | |
| outcome) | | | | | | |
| All-cause mortality | | | | | | |
| up to 180 days from | | | | | | |
| surgery | | | | | | |
| Hospital re- | | | | | | |
| admission within | | | | | | |
| 180 days of surgery | | | | | | |
| Duration of hospital | | | | | | |
| stay | | | | | | |

Table 3 – Process measures

| | Missing data | Missing data | Summary | Summary |
|-------------------------------------|----------------|--------------|----------------|-----------|
| | (intervention) | (control) | measure | measure |
| | | | (intervention) | (control) |
| Consultant led decision to operate | | | | |
| When consultant led decision to | | | | |
| operate, did this consultant | | | | |
| personally review patient at time | | | | |
| of decision? | | | | |
| Preoperative documentation of risk | | | | |
| Time from decision made to | | | | |
| operate to entry into operating | | | | |
| theatre | | | | |
| Patient entered operating theatre | | | | |
| within time-frame specified based | | | | |
| on their urgency level (i.e. <2 | | | | |
| hours, 2-6 hours, 6-18 hours, or | | | | |
| >18 hours) | | | | |
| Consultant surgeon present in | | | | |
| operating theatre | | | | |
| | | | | |
| Consultant anaesthetist present in | | | | |
| operating theatre | | | | |
| Goal directed fluid therapy used | | | | |
| during surgery | | | | |
| Arterial leatete measured at and of | | | | |
| | | | | |
| surgery | | | | |
| Critical care admission immediately | | | | |
| after surgery | | | | |
| | | | | |

Appendix 2: Determining eligibility criteria in NELA dataset

Inclusions/exclusion criteria

Inclusion criteria

- Included on the NELA database
- Age 40 years and over
- Undergoing non-elective surgery
- Undergoing open abdominal surgery
- Admitted to hospital during the 85 week trial period from March 3rd 2014, to Oct 19th, 2015

Exclusion criteria

- Data previously included in the EPOCH trial
- Laparotomy to treat complications of recent elective surgery
- Simple appendicectomy
- Gynaecological laparotomy
- Surgery related to organ transplant
- Laparotomy for traumatic injury

Identifying eligible patients from the NELA dataset

| Inclusion criteria | NELA field ID | NELA Data item | Possible values | Patient included if NELA data item: |
|---|---------------|--|------------------------------------|---|
| Age 40 years and over | 1.4 | Age on arrival | Any age | ≥40 |
| Undergoing non- elective surgery | | | | Elective surgery cases not collected by NELA |
| Undergoing open | 5.4 | Procedure | -Open | Open, Laparoscopic |
| abdominal surgery | | approach | -Laparoscopic | converted to open, or Laparoscopic assisted |
| | | | -Laparoscopic converted to open | |
| | | | -Laparoscopic assisted | |
| Admitted within 85 week period from March 3 rd , 2014 to | 1.9 | Date and time patient admitted to this | Any date | From March 3 rd 2014 to Oct 19 th , 2015 (inclusive) |
| Oct 19 th , 2015 | | hospital | | |

Identifying ineligible patients from the NELA dataset

| Exclusion criteria | NELA field ID | NELA Data item | Possible values | Patient excluded if NELA |
|--|---------------|------------------------|---|--|
| | | | | data item: |
| Laparotomy to treat complications of recent elective surgery | 5.1 | Type for procedure | -First surgical procedure after admission -Surgery for complication of previous surgical procedure within same admission | Surgery for complication of previous surgical procedure within same admission |
| | 5.2 | Indication for surgery | -Planned relook -Peritonitis -Perforation -Abdominal abscess | Planned relook |
| | | | -Anastomotic leak | |
| | | | -Sepsis (other) | |
| | | | -Intestinal obstruction | |
| | | | -Haemorrhage | |
| | | | -Colitis | |
| | | | -Abdominal wound dehiscence | |
| | | | -Abdominal compartment syndrome | |

| | | -Other | |
|-------------------------------------|--|--------|-----------------------|
| Simple appendicectomy | | | Not collected by NELA |
| Gynaecological laparotomy | | | Not collected by NELA |
| Surgery related to organ transplant | | | Not collected by NELA |
| Laparotomy for traumatic injury | | | Not collected by NELA |

Patients included in the main analyses for the primary, secondary, and process measure outcomes

The following algorithm will be used to determine which patients will be included in the main analysis for each outcome. Briefly, eligible patients who are recorded on the NELA database, who have not presented to hospital in the 5 week period immediately after implementation of the intervention, and who have available outcome data will be included in the analysis.

Algorithm:

Patients will be included if:

- 1.4 ≥ 40; and
- 5.4 = Open, Laparoscopic converted to open, or Laparoscopic assisted; and
- 1.9 is between March 3rd 2014 and October 19th 2015 (inclusive); and
- 1.9 is not between the date of implementation (based on the randomisation list) and 35 days after the implementation date; *and*
- $5.1 \neq$ Surgery for complication of previous surgical procedure within same admission; and
- 5.2 ≠ Planned relook; and
- Patient has not presented to a hospital that has merged with other hospitals *after* the date of the merge; *and*
- Outcome variable is not missing

If any of the above data fields for the eligibility criteria are missing, the patient will be excluded from analysis.

Evaluating the effect of the intervention over time

This analysis will include the same set of patients as in the primary analyses above, but will additionally include patients who presented during the 5-week period immediately after implementation, i.e. the algorithm will be the same as above, except the criteria *"1.9 is not between the date of implementation (based on the randomisation list) and 35 days after the implementation date"* will be removed.

Inclusion of other patient populations which may be affected by the intervention

Patients will be included if:

- 1.4 < 40 or 5.4 = Laparoscopic; and
- 1.9 is between March 3rd 2014 and October 19th 2015 (inclusive); and
- 1.9 is not between the date of implementation (based on the randomisation list) and 35 days after the implementation date; *and*
- $5.1 \neq$ Surgery for complication of previous surgical procedure within same admission; and
- 5.2 ≠ Planned relook; and
- Outcome variable is not missing

